6.4.1.2 Primary Safety Analyses

The primary estimator is the ratio of incidence proportions of the primary safety endpoint observed in participants who are under treatment with BAY 2433334 (all doses pooled) and the active comparator for up to 12 weeks with corresponding 90% confidence interval.

The (crude) incidence proportion of the primary safety endpoint is defined as the number participants with an event in 12 weeks while the participant is under exposure of study drug (counting treatment according to the treatment emergent data scope) divided by the number of participants in the treatment arm who took at least one dose of study drug, (the SAF population) i.e.

 $\widehat{CI}_{A} = \frac{\#Participants \text{ with an event}}{\#Participants \text{ that took at least one dose of study drug }A}.$

These incidences proportions will be estimated for BAY 2433334 arm (all doses pooled) and the apixaban arm. The main estimator for this study is the ratio of the (crude) incidence proportions

$$\widehat{CIR} = \frac{\widehat{CI}_{BAY \ 2433334}}{\widehat{CI}_{Apixaban}}$$

The corresponding 90% two-sided confidence interval will be calculated using the Farrington-Manning score for an exact confidence interval. The calculation of the ratio of crude incidences and the confidence intervals will be done by using SAS code corresponding to the following:

Taking the time under risk into account, the exposure-adjusted incidence rate will be calculated for each treatment arm with an 90% confidence interval.

The exposure-adjusted incidence rate will be expressed a "subjects with an event – per 100 participant years". For that the following formula is used:

 $IR_{adj} = \frac{\#Participants with an event}{\sum time under treatment (in days)/(100 * 365.25)}$

The 90% confidence interval for the exposure-adjusted IR will be computed as

$$\left[\frac{IR_{adj} * \chi^2(0.05; 2e)}{2e}; \frac{IR_{adj} * \chi^2(0.95; 2e)}{2e}\right]$$

with $\chi^2(q; 2e)$ the q quantile of a chi square distribution with 2e degrees of freedoms and e the number of participants with an event. (Nelson 1982)

In addition to the main analysis, time-to-first-event analyses taking competing events into account will be performed. For that Aalen-Johansen estimates for the cause specific cumulative risk will be presented.

The competing events for the primary safety endpoint are Death (all causes) and premature discontinuation.

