The cumulative incidence risk, i.e. the probability of having a specific event E at or before a timepoint t, $P(T \le t, E = 1)$, will be estimated for time-to-event endpoints by Aalen-Johansen estimators with the competing event as defined in section 6.2.

The difference of the Aalen-Johansen estimators at day 85 (week 12) between BAY 2433334 treatment and Apixaban will be presented with a 90% confidence interval.

As the Aalen-Johansen estimator is approximately normal distributed (Aalen, Borgan and Gjessing 2008), the difference of Aalen-Johansen estimators is approximately normal distributed. Thus, the two-sided 90% confidence interval is obtained via:

Page: 21 of 25:

$$\left[(\widehat{A}J^{BAY}(85) - \widehat{A}J^{Apixaban}(85)) \pm z_{0.95} \sqrt{\sigma^2(\widehat{A}J^{BAY}(85)) + \sigma^2(\widehat{A}J^{BAY}(85))} \right]$$

with $\widehat{AJ}^{TRT}(85)$ the Aalen-Johansen estimator for treatment TRT at day 85, $z_{0.95}$ the 95% quantile of the standard normal distribution and $\sigma^2(\widehat{AJ}^{TRT}(85))$ the estimated variance of the Aalen-Johansen estimator at day 85, estimated with the Aalen method.

All analyses will be done for the pooled doses of BAY 2433334 and for each of the two doses.

csHRs will be calculated for the respective event and the competing event. Gray's test of equivalence of the cumulative incidence functions, stratified by prior usage of NOAC, will be performed. The cause specific hazard ratios and the corresponding confidence intervals will be estimated on separate models for the pooled doses of BAY 2433334 and each comparison (if applicable). No comparison of the different doses of BAY 2433334 is planned.

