6.4.1.3 Secondary Safety Analyses

The secondary safety estimands are the ratios of the proportions of participants experiencing the individual endpoints within 3 months, comparing pooled doses of BAY 2433334 and comparator drug apixaban in adult participants with AF who have taken at least one dose of study intervention (BAY 2433334 or apixaban, the comparator drug), while the participant is alive and exposed to study intervention for each of the endpoints:

- all bleeding
- ISTH major bleeding
- ISTH clinically relevant non-major bleeding
- ISTH minor bleeding.

The main analyses will follow the main estimation for the primary safety endpoint. In treatment arms with 3 or more events, in addition exposure-adjusted incidence rates and Aalen-Johansen estimators will be presented.

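### The 90% interval for the day-85 risk difference counts the BAY variance twice and omits apixaban's; it is too narrow when BAY bleeds less and its group is at least as large

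*SAP*

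**What the plan says.** Section 6.4.1.2 makes the crude incidence ratio the main estimator for the primary bleeding endpoint. It then adds supplementary work: "In addition to the main analysis, time-to-first-event analyses taking competing events into account will be performed". Part of that is an absolute comparison: "The difference of the Aalen-Johansen estimators at day 85 (week 12) between BAY 2433334 treatment and Apixaban will be presented with a 90% confidence interval".

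The section argues that the difference of the two estimators is approximately normal, so "the two-sided 90% confidence interval is obtained via" a formula of the form estimate ± z × standard error. The estimate is BAY minus apixaban, and z is the 95% normal quantile. The variance under the root is "\sigma^2(\widehat{A}J^{BAY}(85)) + \sigma^2(\widehat{A}J^{BAY}(85". The legend defines the variance symbol for a generic treatment TRT, as "the estimated variance of the Aalen-Johansen estimator at day 85, estimated with the Aalen method".

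The formula serves more than one comparison: "All analyses will be done for the pooled doses of BAY 2433334 and for each of the two doses". The text at hand gives no other formula for this difference. The PROC LIFETEST code in section 6.2 covers the Aalen-Johansen estimators and Gray's test and shows no between-arm difference.

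**The concern.** The two randomised groups are independent, so the variance of the difference is V_BAY + V_Apix. The printed expression is 2 × V_BAY. Apixaban's sampling error therefore never enters an interval about a difference from apixaban, and the stated 90% level is not what the formula delivers.

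The direction of the error depends on which variance is larger. With risks below 50% and a BAY group at least as large as the apixaban arm, lower bleeding on BAY means V_BAY < V_Apix, and the interval is too narrow. That is the result the study hopes to see, so the interval would overstate certainty about a benefit. If V_BAY is the larger, as for a single dose that bleeds more than apixaban with equal arms, the interval is too wide and understates certainty about harm.

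This is the only absolute risk difference with a confidence interval that the SAP text describes for the primary bleeding endpoint, so readers who want the effect in percentage points would rely on it.

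**Working it through.** **Inputs from the SAP (6.4.1.2).** Two-sided 90% interval; z(0.95) = 1.645, which is the right critical value; point estimate BAY minus apixaban; printed variance 2 × V_BAY.

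**Assumptions.** The SAP states neither allocation nor event rates. I take equal arm sizes (pooled 2:1, single dose 1:1), an apixaban risk of 3% and 5%, and 250 per arm where an absolute size is needed. V is approximated by p(1 − p)/n, that is, no censoring before day 85.

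**Formulas.**
- Width ratio, printed to correct: R = sqrt(2·V_BAY / (V_BAY + V_Apix)).
- Approximate coverage of the printed interval: 2·Φ(1.645·R) − 1.
- The nominal 90% is reproduced only when R = 1, that is, V_BAY = V_Apix.

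**Worked case: apixaban 5%, pooled BAY 2.5%, 250 per arm.**
- V_BAY = 0.025 × 0.975 / 500 = 0.00004875.
- V_Apix = 0.05 × 0.95 / 250 = 0.00019.
- Printed half-width: 1.645 × sqrt(0.0000975) = 1.62 points.
- Correct half-width: 1.645 × sqrt(0.00023875) = 2.54 points.
- R = 1.62 / 2.54 = 0.64; approximate coverage 71%.
- Around −2.5 points, the printed interval is −4.12 to −0.88 and the correct one −5.04 to +0.04.

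**Pooled comparison, 2:1, apixaban risk 3-5%.**

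| Risk ratio BAY/apixaban | Width as share of correct | Approximate coverage |
|---|---|---|
| 0.33 | 54% | 62-63% |
| 0.5 | 64% | 71% |
| 0.75 | 74% | 78% |
| 1 | 82% | 82% |
| 1.5 | 92% | 87% |
| 2 | 99% | 90% |
| 2.5 | 104% | 91% |

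Setting V_BAY = V_Apix at 2:1 gives a break-even risk ratio of 2.07 (apixaban 3%) or 2.13 (5%). Below that the pooled interval is too narrow, including at equal risk, because the pooled group is twice as large.

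**Single dose, 1:1.** At ratio 0.5 the width is 82% of correct, with about 82% coverage. At ratio 1 the formula is right by coincidence. At ratio 2 it is 14-15% too wide, with about 94% coverage.

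**Exact check.** Summing over all outcomes of two binomials with 250 per arm:
- Pooled coverage is 70% at ratio 0.5 and 81-82% at ratio 1; the correct formula gives 89-90%.
- At equal risk the printed pooled interval excludes zero 18-19% of the time instead of about 10%, and lies wholly on BAY's side 11-12% of the time instead of 4%.
- Single-dose coverage at ratio 0.5 is 80-81%.
- For a single dose at twice the apixaban risk, the printed interval shows excess bleeding 37% of the time against 49% for the correct one (apixaban 3%), and 62% against 70% (apixaban 5%).

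**Zero events.** Section 4.5.3 lets these calculations run with 3 events in only one arm. A dose with no events would have an estimated variance of zero, so the printed interval would collapse to a point. The correct formula keeps the apixaban variance.

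**The case against.** The case on the other side is about weight; the algebra is conceded.

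- **It is probably a slip that its context resolves.** The point estimate names both arms and the legend defines the variance for any treatment, so a careful programmer would likely put in the apixaban term. That is fair, and every coverage figure here is conditional on coding the formula as printed. It does not remove the need for a correction: following the text gives a wrong interval, and departing from it silently leaves an undocumented deviation.
- **The text is machine-read.** Symbols are lost elsewhere, for example the minus sign in the change-from-baseline rule in 6.3.2. A whole superscript replaced by another is a less likely reading error, and apixaban is read correctly in the same line. The formula should still be checked against the PDF.
- **The role is limited.** The analysis is supplementary and no decision rule hangs on it, so the zero-exclusion figures describe how a reader might use the interval, not a planned test. This stands.
- **Direction depends on allocation.** At apixaban risk 5% and BAY to apixaban 0.5:1, the width is 101% of correct at ratio 0.5 and 110% at 0.75; at 0.67:1 it is 93% and 103%. The claim that the interval is too narrow therefore needs the condition on group size.
- **The zero-crossing in the worked case is fragile.** It implies 12.5 events in each group. With 12 of 500 against 12 of 250 the correct upper limit is +0.09 points; with 13 against 13 it is −0.01. At 300 per arm both intervals exclude zero. The comparison of widths carries the argument; the crossing does not.
- **Reach beyond the primary endpoint is uncertain.** For secondary endpoints section 6.4.1.3 says only that "in addition exposure-adjusted incidence rates and Aalen-Johansen estimators will be presented", which does not explicitly promise differences with intervals.

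**Conclusion.** The concern holds. As printed, the interval omits the apixaban variance, and its coverage is 90% only if the two variances happen to be equal. With equal arms and an apixaban risk of 3-5%, the pooled interval is too narrow at every risk ratio up to about 2.1. Width ratios do not depend on the absolute sample size, but they do depend on the assumed allocation.

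The error is confined to a supplementary analysis. The crude incidence ratio has its own interval ("The corresponding 90% two-sided confidence interval will be calculated using the Farrington-Manning score for an exact confidence interval"), and neither it nor Gray's test nor the cause-specific hazard ratios use this formula. It should be fixed, but it does not threaten the primary result.

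**What to change.** In section 6.4.1.2, change the second variance term so that the root reads sqrt(σ²(AJ_BAY(85)) + σ²(AJ_Apixaban(85))), after confirming the printed formula in the source PDF. Check the program for the pooled comparison and both single-dose comparisons, and for any secondary or exploratory bleeding endpoint that reuses the interval.

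The cost is a one-term SAP correction and a program check. The interval will usually become wider; the primary analysis does not change.

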6.4.1.3 Secondary Safety Analyses

The secondary safety estimands are the ratios of the proportions of participants experiencing the individual endpoints within 3 months, comparing pooled doses of BAY 2433334 and comparator drug apixaban in adult participants with AF who have taken at least one dose of study intervention (BAY 2433334 or apixaban, the comparator drug), while the participant is alive and exposed to study intervention for each of the endpoints:

- all bleeding
- ISTH major bleeding
- ISTH clinically relevant non-major bleeding
- ISTH minor bleeding.

The main analyses will follow the main estimation for the primary safety endpoint. In treatment arms with 3 or more events, in addition exposure-adjusted incidence rates and Aalen-Johansen estimators will be presented.

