4.5.3 Time-to-Event variables

For the treatment emergent data scope, the time from first intake of study drug to an event is of interest. The time to an event (in days) will be derived the following:

Date of Event – Date of first study drug intake + 1.

For time to event variables in the intention-to-treat (ITT) data scope the time from randomization to an event is of interest. The time to an event (in days) will be derived the following:

Date of Event – Date of randomization + 1.

Survival functions, incidence rates and cumulative hazard calculations will be done only for endpoints with at least 3 events in at least one treatment arm. (Cause specific) hazard ratios (csHR) will be calculated only if in addition at least 1 event in each of the compared treatment arm occur.

If treatment arms are pooled the number of events needed applies on the pooled arm not on each treatment arm.

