6.4.2 Subgroup analyses

For the primary endpoint and the endpoint all bleeding, subgroups analyses will be done for the following subgroups:

- Treated with NOAC at randomization (yes/no)
- Atrial fibrillation paroxysmal, persistent/permanent
- Weight (<60; 60-90; >90 kg)
- Age Group (< 65 years, 65 75 years, > 75 years)
- eGFR: <50; 50-80; >80 mL/min
- Risk factors for apixaban dosage (0-1, 2-3)
- Sex
- Race: White, Black, Asian, other
- Region: North America; Western Europe; Eastern Europe; Asia (Japan)
- Stroke or TIA prior to enrollment (yes/no)
- Treated with mild and moderate CYP3A4 inhibitors + inducers at randomization (yes/no)
- CHA2DS2VASc-Score (2&3 vs. > 3 for male participants, 3&4 vs. >4 for female participants)

For these subgroups descriptive tables of crude incidence will be presented. In treatment arms with 3 or more events exposure-adjusted incidence rates will be presented.

Comparison between treatment arms is only planned for the following subgroups:

- Treated with NOAC at randomization (yes/no)
- Stroke or TIA prior to enrollment (yes/no)
- Atrial fibrillation paroxysmal, persistent/permanent
- Risk factors for apixaban dosage (0-1, 2-3)

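### The SAP sets the three-event display threshold per endpoint in section 4.5.3 but per arm in sections 6.4.1.3 and 6.4.2, and does not say which prevails

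*SAP*

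**What the plan says.** The general rule is in SAP section 4.5.3: "Survival functions, incidence rates and cumulative hazard calculations will be done only for endpoints with at least 3 events in at least one treatment arm". For cause-specific hazard ratios it adds a second condition: "hazard ratios (csHR) will be calculated only if in addition at least 1 event in each of the compared treatment arm occur". On pooling it states: "If treatment arms are pooled the number of events needed applies on the pooled arm not on each treatment arm".

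Section 6.4.1.3, on secondary safety endpoints, first makes the crude proportions and their ratio the main analysis, with no event threshold: "The main analyses will follow the main estimation for the primary safety endpoint". It then sets a threshold for the supportive results: "In treatment arms with 3 or more events, in addition exposure-adjusted incidence rates and Aalen-Johansen estimators will be presented".

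Section 6.4.2, on subgroups for the primary endpoint and all bleeding, again has no threshold for crude incidence: "For these subgroups descriptive tables of crude incidence will be presented". It then adds: "In treatment arms with 3 or more events exposure-adjusted incidence rates will be presented". It does not mention Aalen-Johansen estimates.

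For the primary endpoint overall, section 6.4.1.2 gives the exposure-adjusted rate for each arm and sets no arm-level threshold. Its 90% interval uses chi-square quantiles with 2e degrees of freedom, where e is the number of participants with an event. Section 6.4.1.4 says that the exploratory TIMI and BARC endpoints are handled like the other bleeding endpoints, so they may take over the arm-level rule.

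**The concern.** The same number, three, is applied to two different units. In section 4.5.3 the endpoint qualifies or does not. In sections 6.4.1.3 and 6.4.2 each arm qualifies or does not. Two programmers who start from different sections would produce different tables from the same data.

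The arm-level version also makes the display of an arm's result depend on that result. An arm with 0, 1 or 2 events gets no exposure-adjusted rate with its interval and, for secondary endpoints, no Aalen-Johansen estimate. Any supportive Aalen-Johansen difference from apixaban, of the kind described for day 85 in section 6.4.1.2, then cannot be formed for that arm.

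The SAP expects low bleeding on BAY 2433334, so the withheld arms would more often be the individual BAY 2433334 doses. In a dose-finding study, the supportive picture would then be thinnest for the doses with the fewest bleeds.

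**Working it through.** The SAP gives no sample size, event risk or display probability, so there is no figure of its own to reproduce. The check has three steps.

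**Step 1: apply both rules to example counts.** The endpoint-level column assumes that all arms are shown once the endpoint qualifies.

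| Apixaban / dose A / dose B | Endpoint-level rule (4.5.3) | Arm-level rule (6.4.1.3) | Pooled BAY 2433334 count |
|---|---|---|---|
| 3 / 2 / 1 | all three arms | apixaban only | 3, shown |
| 3 / 0 / 0 | all three arms | apixaban only | 0, withheld |
| 5 / 2 / 2 | all three arms | apixaban only | 4, shown |
| 6 / 3 / 1 | all three arms | apixaban and dose A | 4, shown |

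The rules differ whenever one arm has at least 3 events and another has 0 to 2.

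**Step 2: how often this would happen.** Assumptions, none of them from the SAP: 250 participants per arm, independent binomial counts, apixaban risk 1%, 2% or 4%, and a risk ratio of 0.5 for each dose.

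Let a = P(apixaban has at least 3 events), b = P(one BAY 2433334 dose has fewer than 3), and c = P(pooled BAY 2433334, n = 500, has fewer than 3).

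- Apixaban shown, at least one dose withheld: a × [1 − (1 − b)²]
- Apixaban shown, pooled BAY 2433334 withheld: a × c
- Apixaban withheld, at least one dose shown: (1 − a) × (1 − b²)

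| Apixaban risk | a | b | c | Dose withheld | Pooled withheld | Reverse |
|---|---|---|---|---|---|---|
| 1% | 0.457 | 0.869 | 0.543 | 45% | 25% | 13% |
| 2% | 0.878 | 0.543 | 0.123 | 70% | 11% | 9% |
| 4% | 0.998 | 0.122 | 0.003 | 23% | 0.3% | 0.2% |

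For the first row: 0.457 × [1 − 0.131²] = 0.449; 0.457 × 0.543 = 0.248; 0.543 × [1 − 0.869²] = 0.133.

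With 150 to 350 per arm, apixaban risk 1% to 4% and risk ratio 0.33 to 0.67, the first probability runs from about 1% to 85%. With a risk ratio of 1 and 250 per arm it is 36% at 1% risk, against 38% for the reverse. At 2% risk the two are 20% and 12%. Much of the tilt towards withholding a BAY 2433334 dose therefore comes from the assumed lower risk.

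**Step 3: what the withheld rates would look like.** Assume 250 participants each treated for 12 weeks (84 days): 250 × 84 / 365.25 = 57.5 participant-years. Rates are per 100 participant-years, with 90% limits.

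| e | Rate | SAP interval (2e df) | Upper limit with 2e+2 df |
|---|---|---|---|
| 0 | 0 | undefined | 5.21 |
| 1 | 1.74 | 0.09 to 5.21 | 8.25 |
| 2 | 3.48 | 0.62 to 8.25 | 10.95 |
| 3 | 5.22 | 1.42 to 10.95 | 13.49 |

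The SAP formula gives an interval at 1 and 2 events. Only zero events need a new rule. If 2e+2 were used only in sparse arms, an arm with 2 events and an arm with 3 would share the upper limit 10.95, so the method should be the same in every arm.

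**The case against.** The strongest reply is that the sections do not strictly conflict. Section 4.5.3 restricts the calculations to qualifying endpoints ("only for endpoints with at least 3 events in at least one treatment arm"). That is a necessary condition and does not promise that every arm is then shown. The later sections can be read as stricter specific rules, and both can be followed at once. This stands as logic: a reader might infer a flat contradiction, and the text does not support one. But the SAP does not say that the later sections tighten the general rule, so the choice is left to whoever programs the tables.

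A reader might also infer that low-bleeding arms vanish, or that apixaban is left without a comparator. The documents do not support this. Crude proportions are kept for every arm, and the main secondary ratio has no event threshold. The secondary estimands compare pooled BAY 2433334 with apixaban, and the pooled arm is counted as one, so it falls below three less often. The subgroup analyses do not include ISTH major bleeding, and section 6.4.2 restricts rates only, not cumulative incidence.

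A further inference would be that a hazard ratio at 3 versus 1 events would be reported while the rate of the one-event arm is withheld. Section 4.5.3 would allow that hazard ratio, but section 6.4.1.3 does not name hazard ratios among its additional analyses, so this mismatch is uncertain.

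Finally, withholding unstable estimates from sparse arms has a practical purpose, since the SAP interval does not exist at zero events. That supports defining the zero case. It does not justify two different thresholds.

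**Conclusion.** The point holds as an unreconciled inconsistency in supportive displays. The threshold is per endpoint in section 4.5.3, per arm for exposure-adjusted rates and Aalen-Johansen estimates in 6.4.1.3, and per arm for exposure-adjusted rates only in 6.4.2. The overall primary analysis, the crude proportions and the main pooled ratio do not change.

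The practical effect falls mainly on the single-dose arms. If the true risk is halved, a dose is more likely to be withheld while apixaban is shown than the reverse, in all three scenarios. These sizes rest on assumed arm sizes and risks and vary widely with them. They show that the discrepancy could plausibly affect the tables; they do not predict how often it will. It is worth correcting because it is cheap and because the display of an arm should not depend on that arm's own result.

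**What to change.** In sections 6.4.1.3 and 6.4.2, replace the arm-level condition with the endpoint-level rule of 4.5.3. If any arm, or the pooled BAY 2433334 arm, reaches 3 events for an endpoint, show the supportive results for every arm. In 6.4.2, apply the rule to the endpoint within each subgroup level, and say so. State in 4.5.3 that a qualifying endpoint is shown for all arms, so that the condition is no longer only a necessary one.

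Compute the rate interval in all arms with the exact Poisson form: lower limit from 2e degrees of freedom, set to 0 when e = 0, and upper limit from 2e+2 degrees of freedom. One method then covers every arm, including those with no events. Section 6.2 uses the same 2e formula for efficacy rates and could be aligned.

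The cost is a few SAP sentences, a small formula change and the removal of a display filter; no new data are needed. Intervals in sparse arms will be wide, and upper limits rise in the other arms too (at 3 events in the example, from 10.95 to 13.49 per 100 participant-years).
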